- Any lack of compliance to the study procedures which can compromise the safety of the patient and/or study progress and, in particular, for the investigational group only, the lack of safe and competent use of the automated insulin delivery system in both open and closed-loop features.
- Discontinuation of one of the investigational medical devices during the initiation and/or run-in periods.
- Less than 70% of CGM data recorded during selection period after having retried for an additional 14 days period of CGM recordings.
- Patient's inability to attend study visits, Patient's consent withdrawal, Death.

In these above mentioned cases, the patient will be withdrawn and replaced by another patient who will undergo the study protocol in the same study group if the withdrawal occurs before D3. The "end of study" module of the e-CRF (detailed in section VI.6) will be completed accordingly by the investigator and the date and reason of premature withdrawal will be reported in both the e-CRF and the patient's medical file. These withdrawn patients will return to their usual care therapy i.e., multiple daily injection insulin therapy and nursing care.

V - INVESTIGATIONAL THERAPEUTIC STRATEGY

The study investigational therapy is composed of an automated insulin delivery system made up 2 medical devices and of a tailored home healthcare provider service.

V.1 - Overview of IMD: AN AUTOMATED INSULIN DELIVERY SYSTEM

An automated insulin delivery system uses an automated insulin delivery pump with an automated insulin delivery algorithm and an integrated CGM (iCGM) data to adjust basal insulin delivery and deliver automatic insulin correction boluses. The study automated insulin delivery pump is the Tandem t:slim X2 insulin pump in which the automated insulin delivery algorithm is directly implemented into the pump to form one medical device: the Tandem t:slim X2 insulin pump with the Control-IQ technology. The iCGM data will be transmitted from the Dexcom G6 Continuous Glucose Monitoring (CGM) system. Thus, the study automated insulin delivery system made up of 2 medical devices are:

- The Tandem t:slim X2 Insulin Pump with Control-IQ technology, hereafter entitled the "Pump".

 The Dexcom G6 Continuous Glucose Monitoring (CGM) system (CE marking, class IIb), hereafter entitled the "CGM".

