- For patients randomized to the control group: o The Dexcom G6 sensor will be removed and other parts i.e., receiver and transmitter, collected.
 - The patient will be reminded of the installation of a CGM for 20 days at Day 70.
 The patient will be provided with the schedule of visits at home and at the hospital, with the patient diary
- For patients randomized in the investigational group: Pump will be installed.
 - Patient visit will include 2 nights at hospital for patient observation following the set-up of the Dexcom G6 CGM system with the Pump in open mode.
 - The patient (and the caregiver if applicable) will be trained to the use of the Pump and CGM in open mode, specifically on the management of alarms or alerts on the pump and on meal information entry into the pump for bolus insulin delivery (always the same value to facilitate the entry and avoid carbohydrate calculation). Patients will be provided with a short notice describing the management of meals announcement before leaving hospital.
 - After 48h of observation, the Investigator will ensure that the patient (or the caregiver) is able to go back home and follow the instructions for study continuation, and plan the date of the next visit at the hospital to initiate the

Run-in period. Otherwise, the patient will be withdrawn from the study and replaced.

- The patient will be reminded of the next steps of the protocol and will be provided with the schedule of visits at home and at the hospital, with the patient diary
- The investigator will fill in the e-CRF.
- During the next weeks, the investigator will have access to patient's glycaemic data through the cloud-based t:connect® platform and will be trained by the HHP to the display and exploitation of data on the t:connect® platform. The investigator will receive the report from the HHP following his/her visit at patient home.
- o After Visit 1, the investigator will complete the e-CRF

VI.3.2 - ROLES OF THE HOME HEALTHCARE PROVIDER (HHP)

Patients randomized in the control group:

- The HHP will attend the visit at the hospital to collect the Dexcom G6 CGM devices, the dedicated laptop and fill the related certificate.
- The HHP will contact the family nurse to plan the date for the installation of the Dexcom G6 CGM system at Day 70 at the patient's home.
- The HHP will remind the patient to report adverse events and/or device deficiencies/failure in the patient diary.

Patients randomized in the investigational group:

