Table 1: Estimated sample size needed to show the statistical significance of a difference Δ in TIR at D90 varying from 14% to 24% at the 5% level with a power of 90%

| Δ | Number of assessable patients (+10.0%) | % Loss | Number of patients to recruit by group |
|-----|--|--------|--|
| 14% | 31 | 25.0% | 42 |
| 15% | 27 | 25.0% | 36 |
| 16% | 25 | 25.0% | 34 |
| 17% | 21 | 25.0% | 28 |
| 18% | 19 | 25.0% | 26 |
| 19% | 17 | 25.0% | 23 |
| 20% | 16 | 25.0% | 22 |
| 21% | 15 | 25.0% | 20 |
| 22% | 14 | 25.0% | 19 |
| 23% | 13 | 25.0% | 18 |
| 24% | 11 | 25.0% | 15 |

X.2 - DATA SETS ANALYSED

X.2.1 - PATIENTS DATA SETS

The five following data sets analysed will be considered and exhaustively defined prior to the database lock:

- [1] The Selected data set will include all patients who signed an informed consent.
- [2] The Randomised Intention-to-treat (ITT) data set will include all patients who were randomised to study IMD.
- [3] **The Safety data set** will include all randomised patients continuing their study participation at the end of their initiation visit (V1).

- [4] The modified Intention-To-Treat (ITT) efficacy data set will include all patients from the safety data set with at least 3 days with ≥ 70% of non missing data points recording at baseline (selection period), as well as at the end of the study (planned from D70 to D90).
- [5] **The Per Protocol (PP) data set** will include all patients in the modified ITT efficacy data set who completed the 90-day study period without any major protocol deviation.

Safety analysis will be performed on the safety data set.

Efficacy parameters will be analysed in the modified ITT efficacy data set. The primary efficacy endpoint will also be analysed in the PP data set, the PP analysis serving as sensibility analysis.

According to ICH recommendation, modified ITT efficacy and PP analyses will be conducted according to the IMD assigned by the IWRS.

Safety analyses will be conducted according to the IMD actually equipped with rather than according to the IMD assigned.

The definition of the data sets analysed will be finalized during the final Data Review Meeting (DRM), before the database lock. During this DRM, all protocol deviations encountered throughout the study will be reviewed and their consequences on the efficacy evaluations performed will be evaluated.

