This summary table will also be provided for Serious Adverse Events (SAEs) separately.

The number and percentage of patients with at least 1 SEAE will be tabulated by study group, System Organ Class (SOC) and Preferred Term (PT) on the safety data set, as well as:

- the number and percentage of patients with at least 1 most common SEAE (defined as those occurring in at least 5.0% of the patients from the safety data set), if it appears to be relevant,
- the number and percentage of patients with at least 1 SEAE by most severe intensity,
- the number and percentage of patients with at least 1 SEAE by worst recorded relationship to the IMD,
- the number and percentage of patients with at least 1 SEAE by worst recorded relationship to investigation procedures.

The number and percentage of patients with at least 1 SEAE will also be tabulated by study group and SOC only on the safety data set.

For the overall evaluation of AEs (including counting of the number of AEs reported), recurring AEs (i.e., AEs classified under the same Preferred Term (PT)) for a given patient in a given period will be counted only once for the patient concerned in the period concerned.

If relevant, the number and percentage of patients with at least 1 SAE will be tabulated by study group, System Organ Class (SOC) and Preferred Term (PT), separately from all AEs, in a second step.

Moreover, SEAEs occurring during the Run-in period (which only concerns patients allocated to the investigational group) will be tabulated in the safety data set separately, if relevant, or they will be listed if too few patients are concerned.

All SAEs reported throughout the study (i.e., from the date of the selection visit (VO) onwards), all AEs leading to study premature withdrawal (which constitute significant AEs) and deaths if applicable will be listed separately by study group. They will be exhaustively described on an individual basis, including all reported information in the section devoted to AEs in the e-CRF, as well as their start date (i.e., both (1) the time interval between the date of the selection visit (VO) and the occurrence of the AE and (2) the timing of onset of the AE in relation to DO), and duration of the AE.

Adverse Device Effects and Device Deficiencies will be listed separately and they will be exhaustively described on an individual basis, in a similar manner to SAEs, if relevant.

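### The safety set is fixed at the end of V1, so a device patient who leaves during the in-hospital pump start is missing from the detailed adverse event tables

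*Combined protocol and SAP*

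**What the plan says.** X.2.1 (Patients data sets) defines the safety set as one that "will include all randomised patients continuing their study participation at the end of their initiation visit (V1"), and adds: "Safety analysis will be performed on the safety data set". The same section groups safety analyses by the device the patient actually wore, not the one assigned.

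VI.3.1 describes V1 in the device arm: "Patient visit will include 2 nights at hospital for patient observation following the set-up of the Dexcom G6 CGM system with the Pump". The pump runs in open mode at this stage. After 48 hours the investigator decides whether the patient or caregiver can go home and follow the instructions. "Otherwise, the patient will be withdrawn from the study and replaced". IV.4 adds a further withdrawal reason that can apply in this window: "Discontinuation of one of the investigational medical devices during the initiation and/or run-in periods". It provides for replacement in the same group when withdrawal occurs before D3. Control patients have the sensor removed at V1 and their insulin prescription reviewed, with no pump and no two-night stay.

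X.3.5.2 treats an adverse event as study emergent (SEAE) if it starts on or after the day of V1. It then states that the number and percentage of patients with at least one SEAE "will be tabulated by study group, System Organ Class (SOC) and Preferred Term (PT) on the safety data set", and attaches to that sentence the tables of most common SEAEs, of intensity, and of relationship to the device and to procedures. The table by System Organ Class alone is also placed on the safety set.

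The opening of X.3.5, by contrast, says that exposure and adverse events are tabulated in both the Randomised ITT and the safety sets.

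**The concern.** Whether a patient enters the safety set depends on something that happens after exposure to the pump has begun. The event window opens on the day of V1, but membership is decided at its end. A device patient who stops in between has an event that the plan counts as on-study, while the patient is in neither the numerator nor the denominator of the detailed tables.

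The filter is not balanced. For controls V1 is an ordinary visit, so leaving because of a difficult first exposure to the pump can happen only in the device arm. The tables affected are the ones a reader uses to see which events occurred, how severe they were and whether they were attributed to the device. I.1.5.2 reports that people with type 2 diabetes stop pump treatment more often than those with type 1, mainly over acceptability when it happens before six months. Early failure on the pump is therefore something this trial should show clearly.

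**Working it through.** **Tracing one patient through the rules.** Take a device patient fitted with the pump at V1 who has an event during the 48 hours.

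| Outcome at end of V1 | Study-emergent event? (X.3.5.2) | In safety set? (X.2.1) | In detailed SEAE tables? (X.3.5.2) | Reported elsewhere? |
|---|---|---|---|---|
| Continues | Yes | Yes | Yes | Yes |
| Leaves the study | Yes | No | No | Randomised ITT tabulation (X.3.5); listing if serious or the cause of withdrawal (X.3.5.2); withdrawal summary (X.4) |

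Only the second row is affected.

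**Denominators.** X.1 plans 28 randomised patients per arm. The plan's figure reproduces: n = 2 × (16/17)² × (1.960 + 1.282)² = 18.6, rounded up to 19; 19 × 1.10 = 20.9, rounded up to 21; 21/0.75 = 28 per arm, 56 in total. This point disputes none of these figures; 28 serves only as the size of the device arm.

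**Effect of one or more losses, with replacement.** If k device patients leave during V1 and each is replaced, 28 + k are randomised to the device arm and 28 remain in the safety set. Suppose all k had an event type seen in nobody else. The limits are exact (Clopper-Pearson) 95% limits.

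| k | All randomised device patients | Safety set |
|---|---|---|
| 1 | 1/29 = 3.4% (0.1 to 17.8%) | 0/28 = 0% (upper limit 12.3%) |
| 2 | 2/30 = 6.7% (0.8 to 22.1%) | 0/28 = 0% (upper limit 12.3%) |
| 3 | 3/31 = 9.7% (2.0 to 25.8%) | 0/28 = 0% (upper limit 12.3%) |

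The upper limit for 0/28 is 1 − 0.025^(1/28) = 12.3%.

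**How likely is at least one loss?** The documents give no V1 stop rate, so a range is assumed. The chance that at least one device patient is lost before 28 are retained is 1 − (1 − p)^28.

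| Assumed stop rate p | Chance of at least one loss | Expected number lost, 28p/(1 − p) |
|---|---|---|
| 2% | 43% | 0.6 |
| 5% | 76% | 1.5 |
| 10% | 95% | 3.1 |

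These figures count patients who leave, whatever the reason. The number who leave with an adverse event would be smaller.

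**The case against.** The strongest reply is that the plan reports these patients elsewhere. X.3.5 tabulates adverse events in the Randomised ITT set, which contains everyone lost at V1. The overall summary in X.3.5.2 is not tied to the safety set and includes device-related and procedure-related SEAEs. All serious events, events leading to withdrawal and deaths are listed individually; device effects and deficiencies are listed where relevant. X.4 describes withdrawals in the Randomised ITT set by time, period and reason. All of this stands. A reader might infer that early device harm disappears from the report, or that device safety as a whole will look better than it was. The documents do not support that. What remains is that listings give neither a denominator nor a comparison between arms, and that X.3.5 names two sets where X.2.1 and the detailed tables name one.

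Three other readings are tempting and also go too far.

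- **Everyone harmed at V1 is lost.** No. A patient who has an event and continues is retained, and the event is counted.
- **Early closed-loop failures are hidden.** V1 is open mode. Closed loop starts at V2, so every patient who starts it has already passed the end of V1.
- **The efficacy analysis is affected.** The modified ITT set "will include all patients from the safety data set with at least 3 days" of adequate CGM recording at baseline and again between D70 and D90. A patient who leaves at V1 has no D70 to D90 study recording, so building that set from all randomised patients would give the same people.

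Controls can also leave by the end of V1, because allocation is disclosed by phone beforehand. The imbalance is therefore expected from the design but not absolute.

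**Conclusion.** The point holds in a limited form. The safety set is conditioned on completing V1, the SEAE window opens earlier, and the detailed SEAE tables use only that set. Device patients who leave during V1 are therefore dropped from the tables by class and term, intensity and relationship, and this selection falls mainly on one arm.

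Its size is unknown. With replacement, one such patient turns 1/29 (3.4%) into 0/28 (upper limit 12.3%). That rests on the event type being seen in nobody else; the stop rates of 2% to 10% are assumptions. The effect is on completeness and comparability of descriptive safety tables. No hypothesis test and no part of the primary analysis depends on it. The change is worth making because it is specific and cheap, and because the sections do not agree as they stand.

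**What to change.** In X.2.1, define the safety set by exposure: all randomised patients who started V1, meaning in the device arm those fitted with the pump, grouped by the device actually worn, as the section already provides. In X.3.5 and X.3.5.2, state that every SEAE table is run on this set, so that the three places agree. The Randomised ITT tabulation can stay as a supplement. Using all randomised patients as the safety set is less suitable, since it duplicates the Randomised ITT set and adds patients never fitted with a device to the denominator.

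No change to the modified ITT set is needed on this ground.

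The cost is a few sentences. No new data are required, because adverse events are collected from consent, and X.2.1 leaves the set definitions to be finalised before database lock. The downside for the sponsor is that the device arm's safety figures may look slightly less favourable.

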Database status will be declared as final when all data have been entered, cleaned by the Data Manager, validated by the monitor and the investigator or delegate. After declaration of a final database, the data will be exported from the SQL source database and converted into SAS datasets in the final database, and both databases will be locked and protected from changes. All statistical analyses for the final analysis will be performed on the locked SAS database.

IX.3 - STUDY COMMITTEES

A Data Safety Monitoring Board (DSMB) will be established prior to study start (first visit of first patient). All members will be independent from the Sponsor.

A Data Safety Monitoring Board (DSMB) will review the safety data of the five first patients of each group, then 25 patients having completed the study, and more frequently if judged necessary by the DSMB. The DSMB will make recommendations regarding the continuation, temporary suspension or definitive termination of the clinical study.

Composition, role and frequency of DSMB meetings will be detailed in the separate DSMB Charter.

X - STATISTICAL METHODS

X.1 - SAMPLE SIZE

The primary study objective is to demonstrate that the tested therapeutic strategy is superior to the usual care strategy on the TIR at D90.

The required number of assessable patients can be assessed using the standard formula of comparison of 2 means:

$$n_A = 2 \times \frac{s^2}{\Lambda^2} \times \left(z_{\alpha/2} - z_{power} \right)^2$$

With n_A = number of assessable patients/group, s=standard deviation, and Δ = expected difference between both groups

Based on previous studies [53], the difference between the investigational group and the control group is expected to be between 14% and 24%, and the standard deviation corresponding to the mean TIR is expected to be equal to 16 (identical in both groups).

Based on a difference of 17% in the mean TIR at D90 between the investigational group and the control group, a standard deviation = 16 (identical in both groups) for the mean TIR at D90, a type 1 error (α) = 5.0%, a type 2 error

(β) = 10.0% (statistical power = 90.0%), the sample size estimation yields n=21 valid patients per study group including a 10.0% account for the adjusted analysis (primary analysis adjusted on HbA1c value at baseline and TIR at baseline). Allowing for a 25.0% rate of non-evaluable patients, a total of 56 patients needs to be randomized (28 patients in each study group).

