A deviation will be considered major and thus, resulting to the exclusion of the concerned patient from the Per Protocol data set, when it is likely to bias significantly the interpretation of the efficacy results, especially the primary efficacy endpoint (i.e., the TIR at D90). All other protocol deviations will be considered minor.

A listing of all protocol deviations will be provided for all randomised patients, including the type (major/minor) of protocol deviations according to the decisions made during the DRM. The number and percentage of patients with protocol deviations will be tabulated by study group (and overall) and type of protocol deviations on the modified ITT efficacy data set.

Protocol deviations which will be evaluated will include, but will not be limited to:

- deviations in selection, inclusion and exclusion criteria,
- deviations in dates of visits and assessments, including study premature withdrawals, deviations in the allocation and/or the schedule of the study IMDs equipment.

X.3 - STATISTICAL ANALYSES

A Statistical Analysis Plan (SAP) will be prepared by the CRO and validated by the Sponsor. Its final version will be approved after the DRM. After database lock, statistical analyses will be performed by the CRO under the supervision of the Sponsor with SAS® version 9.2 or higher (SAS institute, North Carolina, USA).

X.3.1 - GENERAL CONSIDERATIONS

Analyses will be adjusted on the HbA1c level at baseline (<10.0% or ≥10.0%) if the study recruitment allows it.

Thorough description of all parameters recorded will be presented separately by study group, using the observed case approach (apart from the primary endpoint as detailed in section VII.1). Summary tabulated results will be provided by group and assessment time/visit, if relevant or they will be replaced by the corresponding individual data listings if too few patients are concerned.

Quantitative variables will be summarized in tables displaying number of patients, means, standard deviations, medians and percentiles when appropriate, and extreme values. When applicable, the Wald two-tailed 95.0% Confidence Interval (95%CI) of the means will be provided.

Qualitative variables will be described in terms of frequencies and percentages of the total number of non-missing recordings described. When applicable, the Agresti-Coull [54] 95%CI of the percentages will be provided.

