- and one table showing the number and percentage of patients with at least 1 metabolic system concomitant treatment with start date at the latest on the day before the initiation visit, by ATC system subgroups (ATC2, ATC3 and ATC4 codes).

X.3.3 - PRIMARY EFFICACY ENDPOINT ANALYSIS

The primary efficacy endpoint is the TIR at D90 for the full 24-h day (as detailed in section VII.1).

The primary analysis of this primary endpoint will be performed on the modified ITT efficacy data set (defined in section X.2.1). The TIR at D90 will be compared between both study groups using a parametric ANalysis of COVAriance (ANCOVA) model with 3 factors: HbA1c category level at baseline, TIR value at baseline as covariate and study group assigned by the IWRS.

This ANCOVA model corresponding to the primary analysis of the primary efficacy endpoint will allow testing the following set of hypotheses:

- H₀ (the null hypothesis of interest): mean TIR values at D90 are equal in the two groups,
- against H₁ (the alternative two-sided hypothesis): mean TIR values at D90 differ between the two groups.

This primary ANCOVA model will be repeated in a secondary supportive step, including the interaction between the HbA1c category level at baseline and the study group as fixed effect, if the study recruitment allows further exploration of the HbA1c category level effect on the TIR at D90.

If this interaction term is significant ($p \le 0.10$) and if it appears potentially relevant from a clinical point of view, further analyses and/or graphs might be produced to interpret this statistically significant interaction.

Both ANCOVA models with and without interaction term (*if relevant*) will be repeated on the TIR at D90 considering the diurnal period (*from 06.00 H to 23.59 H*) and the nocturnal period (*from 00.00 H to 05.59 H*) separately as supportive analyses of the primary efficacy endpoint.

Moreover, all 3 ANCOVA models with and without interaction term (*if relevant*) will be performed in the PP data set to check their robustness.

X.3.4 - SECONDARY EFFICACY ENDPOINTS ANALYSIS

The secondary efficacy endpoints will be analysed in the modified ITT efficacy data set.

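### The within-arm 95% confidence intervals for means are specified as Wald intervals, which in the usual sense cover about 93.6% to 94.0% at the planned arm sizes

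*Combined protocol and SAP*

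**What the plan says.** Section X.3.1 (General considerations) sets the rules for the descriptive tables, which are given separately for each study group: "Quantitative variables will be summarized in tables displaying number of patients, means, standard deviations, medians and percentiles when appropriate, and extreme values". It adds that, where applicable, "the Wald two-tailed 95.0% Confidence Interval (95%CI) of the means will be provided". The synopsis (Statistical analyses) repeats this sentence. Neither place gives a formula or says whether the quantile is normal or t. For percentages, section X.3.1 goes on to name a specific method, Agresti-Coull.

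Arm sizes come from section X.1: "the sample size estimation yields n=21 valid patients per study group including a 10.0% account for the adjusted analysis", and, after an allowance of 25% for non-evaluable patients, "a total of 56 patients needs to be randomized (28 patients in each study group").

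Between-group comparisons are set elsewhere. Section X.3.3 uses a parametric ANCOVA for TIR at day 90. Sections X.3.1 and X.3.4 use ANCOVA (on ranks for non-Gaussian variables), mixed models for repeated measures, or Cochran-Mantel-Haenszel tests for the other efficacy endpoints. Section X.3.5 plans no tests for safety data.

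**The concern.** When the standard deviation is estimated from about 20 to 30 patients, the normal quantile is too small. For normal data, the t quantile with n − 1 degrees of freedom gives exact coverage. An interval built with 1.96 is a little too narrow, and its true coverage falls below the 95% printed in the table heading.

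What is at stake is the accuracy of that label in the within-arm summaries. It matters most for safety variables such as laboratory and blood pressure changes. No tests are planned there, so any interval shown would be the only statement of uncertainty.

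**Working it through.** **Inputs.** All come from section X.1: difference 17 points, SD 16 in both arms, two-sided alpha 5%, power 90%, a 10% allowance for adjustment, 25% non-evaluable. One reading is assumed: Wald means mean ± 1.96·s/√n.

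**Step 1: reproduce the arm sizes.**
- n = 2 × (16²/17²) × (1.960 + 1.282)² = 18.62, rounded up to 19.
- 19 × 1.10 = 20.9, rounded up to 21 evaluable per arm.
- 21 / 0.75 = 28 randomised per arm.

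Both stated figures reproduce. The relevant range is therefore n = 21 (efficacy tables as planned) to n = 28 (all randomised patients).

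**Step 2: coverage of the normal-quantile interval.** For normal data, (mean − μ)/(s/√n) follows a t distribution with n − 1 degrees of freedom. Coverage is therefore 2·F(1.96; n − 1) − 1, where F is the t distribution function. Relative width is t(0.975; n − 1)/1.960, and the half-widths use SD 16.

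| n per arm | t quantile | Coverage with 1.96 | t interval wider by | TIR half-width, 1.96 | TIR half-width, t |
|---|---|---|---|---|---|
| 21 | 2.086 | 93.6% | 6.4% | 6.84 | 7.28 |
| 28 | 2.052 | 94.0% | 4.7% | 5.93 | 6.20 |

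At n = 21: 1.960 × 16/√21 = 6.84 and 2.086 × 16/√21 = 7.28, a difference of 0.44 TIR points. The coverage shortfall is 95.0 − 93.6 = 1.4 percentage points.

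**Step 3: check by simulation.** With 400,000 normal samples of size 21 and SD 16, the 1.96 interval covered the true mean in 93.6% of samples and the t interval in 95.0%.

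**The case against.** The strongest reply is that the text gives no quantile. Section X.3 also foresees a detailed SAP, to be finalised after the data review meeting, which could specify t. That is fair: the use of 1.96 is inferred from one word. But this is the usual meaning of the word, and the plan names its interval for percentages just as specifically. If t is intended, the word misleads; if 1.96 is intended, the label is slightly wrong. The same edit settles both cases.

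A second reply is that the effect is too small to matter: 0.44 TIR points on a descriptive interval that no decision rule uses. The size is right, and it makes this a minor point. It does not make the label correct.

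Three stronger readings are tempting, and the documents do not support them.
- **A reader might infer that these intervals carry the main message of the secondary results, because section X.3.1 calls those results descriptive.** The same section and section X.3.4 plan between-group comparisons for them. The Wald sentence concerns the mean within each arm, not the treatment contrast.
- **A reader might infer that the primary result is affected.** It comes from the ANCOVA in section X.3.3, which does not use this interval.
- **A reader might infer much worse coverage in the HbA1c ≥10.0% stratum.** Coverage does fall as n falls. However, HbA1c category enters the plan as an adjustment factor, no stratum size is given, and no descriptive table by stratum is planned. Further output is only a possibility after a significant interaction. Section X.3.1 also lets individual listings replace tables when numbers are very small.

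**Conclusion.** The point holds as a minor correction of wording. Read in the usual sense, the specified interval for a within-arm mean covers 93.6% at 21 patients and 94.0% at 28, and the t interval is 6.4% and 4.7% wider.

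This rests on three assumptions: the normal quantile is meant, the data are normal, and the numbers per arm are as planned. It applies only where the plan provides an interval for a mean. Type I error, power, the primary conclusion and the between-group comparisons of secondary endpoints do not change.

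Nor should a reader infer that t-based intervals secure 95% coverage for every variable. Time below range is bounded at zero and likely to be skewed, and neither quantile guarantees the nominal level there.

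**What to change.** In section X.3.1 and in the synopsis, replace *Wald* by *Student t-based* for the confidence intervals of means, and carry the same wording into the detailed SAP. Section X.5 already provides for recording such a change there and in the study report.

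The cost is one term in two places and slightly wider intervals, about 0.44 points of half-width for TIR at 21 per arm. Sample size, data collection and the primary analysis stay as they are.
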